4.6.2 Infants Childhood Developmental Milestones

The infant's developmental milestones will be assessed using the Ages and Stages Questionnaire version 3 (ASQ-3), in the domains of communication, gross motor, fine motor, problem solving, and personal-social at Week 6 and Months 2, 4, 6, 9, and 12.

The total score for each domain will be summarized by visit using continuous statistics in the SAFI. In addition, the number and percentage of infants with abnormal scores (Yes/No) will be presented in the SAFI, as per cut-offs below transcribed from the ASQ-3 User's guide.

450.2	Area				
questionnaire	Communication	Gross Motor	Fine Motor	Problem Solving	Personal Social
Month 2	22.77	41.84	30.16	24.62	33.71
Month 4	34.60	38.41	29.62	34.98	33.16
Month 6	29.65	22.25	25.14	27.72	25.34
Month 9	13.97	17.82	31.32	28.72	18.91
Month 12	15.64	21.49	34.50	27.32	21.73

ASQ-3=Ages and Stages Questionnaire version 3.

Values below the respective cut-off will be classified as abnormal (i.e., further assessment with a professional may be needed).

A corresponding listing will be produced.

Only questionnaires assigned to the correct time point will be included in the main analysis. If the wrong questionnaire is used for some time points in >20% infants, a sensitivity analysis will be performed with these data included.

4.6.3 Women's Immunity During Pregnancy

To evaluate humoral immunity to clinically relevant pathogens in mothers during pregnancy. Serum antibody (IgG) titers to immunizations: for measles, mumps, rubella, TT, diphtheria, pertussis, varicella zoster, Streptococcus pneumoniae, HBV and SARS-CoV-2 (along with nucleocapsid and spike protein titers; only for those mothers who have received the vaccine, as per local clinical practice) will be collected in the third trimester (Week 35). This will be presented in the same way as for infant immune response in Section 4.5.3 but for the SAFW population.

A listing with all immune response will be produce.

4.6.4 Women's Disease Activity

To assess disease activity and progression in women, the potential relapse is recorded and EDSS, a neurological examination is performed during pregnancy (Week 24-30 and Week 35), at infusion (if applicable), at early discontinuation and unscheduled visit if applicable. This will be summarized as follows in the FASW:

- Clinical Relapse:
 - Number of relapses before, during pregnancy (defined by LMP) and after pregnancy (defined as after birth) will be summarized in 3-month interval respectively.
 - Number and percentage of women in each category (0, 1, 2, 3 and ≥4) in
 3-month intervals of before/during/after pregnancy.
 - Number of relapses after first OCR and up to 1 year before pregnancy, during pregnancy, up to 1 year after delivery will be presented. Annualized relapse

rate and 95% CI may also be presented if warranted by the number of data points.

- Mean EDSS score in 3-month interval of before/during/after pregnancy. In case of multiple EDSS score at the same visit, the median will be used.
- Change from baseline in EDSS by visit.
- Presence of any clinically significant abnormalities from the neurological examination (Yes, No) by visit
- Type of neurological abnormality (disability progression independent of relapse, MS relapse, signs or symptoms suggestive of Progressive Multifocal Leukoencephalopathy, Other) by visit

MS relapses, EDSS and neurological examination findings will also be listed. Analysis will also be presented for subgroups based on OCR exposure prior to the study as list in Section 4.5.4.

4.6.5 Women's Neuroaxonal Damage

To detect presence of neuroaxonal damage in the mother during pregnancy and postpartum, serum neurofilament light chain (sNfL) levels are measured at baseline (gestational age Week 24-30), gestational age Week 35, at delivery and postpartum (in line with ocrelizumab administration timepoints). Absolute sNfL levels will be log (base 10) transformed. The geometric mean with corresponding 95% CI and change from baseline will be back transformed and presented. Absolute sNfL levels as well as change from baseline based on log back transformed may also be displayed graphically over time, as appropriate.

4.6.6 Infant Evolution of B Cell Levels

To evaluate the evolution of B cell levels between birth and the first year of life, B cell (CD19+ cell, absolute counts and percentage of lymphocytes levels are collected in the infant from week 6 of life to 1 month after the first or second dose of MMR vaccine or Month 13 of age in case MMR vaccine is not planned to be administered.

Summary statistics for the mean absolute values and percentage change from Week 6 will be presented at each visit (Week 6 of life, 1 month after month after the first or second dose of MMR vaccine, Month 13 of age in case MMR vaccine isn't administered) for absolute CD19+ cell counts and percentage of lymphocytes based on the FASI, irrespective of the occurrence of any ICEs identified for the primary endpoint.

Subject profile plots (one line per infant) will be used to display the trajectory of CD19+ cell levels (absolute counts and percentage of lymphocytes) over time in the FASI. The Y axis will be the absolute cell count or percentage of lymphocytes, and the X axis will be age in weeks. Lines will be plotted based on the actual age (i.e., not pooled into age categories). The age-specific LLN and ULN (see Appendix 4) for CD19+ cell counts and percentage of lymphocytes will be overlayed.

All B cell data collected will be listed.

4.7 PHARMACOKINETIC AND PHARMACODYNAMIC ANALYSES

Pharmacokinetic and pharmacodynamic (B cells) analyses for ocrelizumab in the umbilical cord blood at birth and serum are described elsewhere for the secondary endpoint.

4.8 SAFETY ANALYSES

The safety outcome measures comprise the following: incidence and nature of all adverse events (AEs), including findings on vital sign measurements, clinical laboratory tests, and concomitant medications.

The safety analysis will be performed on the safety populations of women (SAFW) and infants (SAFI) separately.

4.8.1 Exposure of Study Medication

Ocrelizumab will not be administered post-baseline until the infant's birth. Treatment with commercial ocrelizumab may be resumed at any time after birth for women who decide not to breastfeed. Some women may decide to resume treatment with ocrelizumab whilst breastfeeding. For those women, treatment with ocrelizumab should be restarted after collection of the infant blood sample at Week 6 of life (±7 days) if possible, but the decision is left to the discretion of the woman and the investigator.

Definitions

Dose: Ocrelizumab dose is given as one infusion or two infusions administered 2 weeks apart. Women will be considered to have received a dose of treatment if at least part of one infusion of that Dose (either Day 1 or Day 15 for dual infusions) was given.

Treatment duration (in weeks) for woman received OCR will be calculated as follows: [(Date of last contact* - Date of first postpartum dose) + 1] / 7

*Earliest 1) date of last OCR dose plus risk window of 6 months (182 days)2) date of death3) Clinical Cut-off Date

Exposure Analysis

The following measures of exposure of ocrelizumab will be summarized in the SAFW using descriptive statistics:

- Number of patients completing each dose type (Dose 1, full dose; Dose 1 split dose #1; Dose 1, split dose #2, Dose 2, full dose; Dose 3, full dose)
- Treatment duration (weeks)
- Number of doses received (Day 1 and Day 15 infusions are considered as one dose)

• Total cumulative dose (mg)

A corresponding listing will be produced.

MS treatment postpartum

- Type of DMT including ocrelizumab use postpartum
- Time (months) between delivery and first postpartum ocrelizumab as continuous and categorical (0-3 months, >3 and ≤6 months, >6 months)
- Number of women who received ocrelizumab dose postpartum
- Number of ocrelizumab doses postpartum
- Time (months) between first and second postpartum ocrelizumab dose

4.8.2 Adverse Events

All summaries of AEs will be presented separately for women and infants based on the respective Safety population. Adverse events will be presented overall and by timepoint (defined below). AEs will also be presented for subgroups based on OCR exposure prior to the study as list below, for infants and women separately:

- In 3-month interval of before/during pregnancy (3-6 months before LMP, 0-3 months before to LMP, during the 1st trimester)
- ≥3 months before to LMP vs <3 months prior to LMP and/or during pregnancy

For each recorded adverse event (AE), the term entered by the investigator describing the event (the "reported term") will be assigned a standardized term (the "Preferred Term" [PT]) and assigned to a superclass term (the "System Organ Class" [SOC]) on the basis of the MedDRA WHO dictionary of terms version 26.1.

Definitions

Infant AE timepoints:

Neonatal (<28 days): AEs with an observed or imputed date of onset before the first 28 days of life.

Infant (≥28days): AEs with an observed or imputed date of onset on or after the 28 days of life.

Women AE timepoints:

Pregnancy: AEs with an observed or imputed date of onset before the infants' birth, i.e. during pregnancy. An AE with a completely missing, non-imputed start date will be assumed to be a pregnancy AE.

Pre-ocrelizumab postpartum: AEs with an observed or imputed date of onset on or after the infants' birth but before the start date of the first postpartum ocrelizumab infusion.

Post-ocrelizumab postpartum: AEs with an observed or imputed date of onset on or after the start date of the first postpartum ocrelizumab infusion.

Imputation of incomplete date: incomplete dates will be imputed as follows:

- If the start date is incomplete:
 - If the day is missing, impute to 01.
 - If the month is missing, impute to January.
 - If the date is completely missing, then the date will remain missing
- If the end date is incomplete:
 - If the day is missing, impute to the last day of the month
 - If the month is missing, impute to December
 - If the date is completely missing, then the date will be missing

Serious Adverse Events (SAEs): all SAEs including serious MS relapses and serious Infusion Related Reactions (IRRs).

Output Conventions

All analyses of AE data will be performed using the PTs unless otherwise specified.

For all summary tables, the AEs will be sorted by SOC (in decreasing order of overall incidence) and then by PT (in decreasing order of overall incidence). At each level of summarization (at least one event, SOC and PT), subjects reporting more than one AE will be counted only once. For AEs by grade (intensity), the highest grade will be reported.

The following summary tables will be generated for mothers and infants separately:

- Overview summary table of AEs, including: total number of subjects with at least one AE, total number of AEs, total number of deaths, total number withdrawn from study due to an AE, and total number of subjects with at least one:
 - AE with fatal outcome
 - SAE
 - SAE leading to withdrawal from treatment in the mother ("Drug Withdrawn" for the "Action taken with ocrelizumab due to SAE/AE" field in the "Adverse Event/IRR" electronic Case Report Form [eCRF] form)
 - SAE leading to dose modification/interruption in the mother.
 - Related SAE

- AE leading to withdrawal from treatment in the mother.
- Time to withdrawal from the study due to an AE from enrollment (in women)
- Time to withdrawal from the study due to an AE from birth (in infants)
- AE leading to dose modification/interruption in the mother.
- Related AE
- Related AE leading to withdrawal from treatment in the mother.
- Related AE leading to dose modification/interruption in the mother.
- AE of Grade ≥ 3
- Infusion related reaction (IRR) in the mother
- Serious IRR in the mother
- Infections (using the MedDRA SOC of 'Infections and Infestations')
- Serious infections
- Serious infections leading to withdrawal from treatment in the mother.
- Adverse Events of Special Interest (AESI):
 - Cases of potential medicine-induced liver injury include an elevated alanine aminotransferase (ALT) or aspartate aminotransferase (AST) in combination with either an elevated bilirubin or clinical jaundice, as defined by Hy's law and in the protocol.
 - Suspected transmission of an infectious agent by the study medicine, as defined in the protocol.

All SAEs, AESIs, AEs leading to withdrawal and deaths occurring during the study will be listed.

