3.1.4 Vaccination Period

Both the mother and the infant will enter an extension phase, which will continue approximately until the infant reaches 13 months of age. This is designed to evaluate whether infants potentially exposed to ocrelizumab during pregnancy are able to mount humoral immune responses to clinically relevant vaccines.

Infant laboratory assessments will be performed 1 month (+30 days) after the first dose of MMR vaccine (if first dose is administered at 11 months of age or later) or 1 month (+30 days) after second dose of MMR vaccine (if first dose is administered before 11 months of age), or at Month 13 of chronological age (+30 days), if MMR vaccine is not planned to be administered (as per local clinical practice, vaccinations may include diphtheria, tetanus, pertussis, Hemophilus influenzae type b [Hib], 13-valent pneumococcal conjugate vaccine [PCV-13], hepatitis B virus [HBV], and MMR). Additionally, infants will continue to be followed up for growth (age-adjusted body length, weight and head circumference) and developmental milestones up to 12 months of age. Growth charts following the World Health Organization (WHO) Child Growth Standards (WHO 2022), absolute values and the Ages and Stages Questionnaire, version 3 (ASQ-3) will be used; other standard measurements recorded by e.g., the pediatrician as part of routine postnatal care may also be used. The time windows for infant growth velocity and child developmental milestone assessments are given in Appendix 6. Post-natal timings of ocrelizumab infusions every 6 months and laboratory/clinical assessments in the mother may occur at different time points than infant assessments. In case the mother decides to switch to another DMT or to stop DMT after birth, no laboratory/clinical assessments will be performed for the mother. However, the infant blood sample 1 month (+30 days) after the first or second dose of MMR vaccine (or at Month 13 of age [+30 days]) will still be collected.

A structured telephone interview will be conducted by site personnel postpartum every 3 months (in-between ocrelizumab infusions) for a general review, and to identify and collect information on any changes in the woman's or infant's health status (including the occurrence of MS relapses in the woman and use of new concomitant medications) and possible adverse events in both the woman and the infant (particularly infections);

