3.2 END OF STUDY AND LENGTH OF STUDY

The end of the study is defined as the date of the last assessment (vaccine response titers measured 1 month [+30 days] after the first or second dose of MMR vaccine, or at Month 13 of age (+30 days) if MMR is not planned to be administered for the last infant.

The total length of the study, from screening of the first woman to the end of the study, is expected to be approximately *33* months. This includes an enrollment period of approximately *16* months and subject participation period of approximately 17 months.

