5.1.2.1 Adverse Event Reporting Period

Investigator will seek information on adverse events at each patient contact. All adverse events subject to the collecting and reporting requirements outlined in this protocol, whether reported by the patient or noted by study personnel, will be recorded in the patient's medical record and in the Adverse Event eCRF.

Adverse events will be reported throughout the study and until the last study visit for both mother and infant. After this period, the investigator should report any serious adverse events that are believed to be related to prior study drug treatment. Adverse events that

occur in a pregnant woman pre- and post- study should be reported to the marketing authorization holder (MAH), as a follow up spontaneous pregnancy report to the initially spontaneously reported pregnancy, by following the standard pharmacovigilance reporting process for post-marketing pregnancy cases.

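### The end date of maternal postpartum treatment duration (SAP 4.8.1) omits the woman's own last study contact, so some dosed women are credited time after routine AE collection has stopped

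*SAP*

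**What the plan says.** SAP 4.8.1 computes treatment duration in weeks, for women who receive ocrelizumab postpartum, as "Date of last contact* - Date of first postpartum dose) + 1] / 7". The footnote defines the end date as the earliest of three: the "date of last OCR dose plus risk window of 6 months (182 days", the date of death, and the Clinical Cut-off Date. Those three dates are the whole list. The result is summarised descriptively in the exposure table.

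Protocol 5.1.2.1 sets the period of routine AE collection: "Adverse events will be reported throughout the study and until the last study visit for both mother and infant". Beyond that, collection narrows: "After this period, the investigator should report any serious adverse events that are believed to be related to prior study drug treatment".

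Protocol 3.1.4 describes the phase that mother and infant enter after Week 6 as one "which will continue approximately until the infant reaches 13 months of age". The restart of ocrelizumab is not tied to a date. Protocol 4.3.2.1 allows it at any time after birth for women who do not breastfeed, and SAP 4.8.1 plans to summarise "Time (months) between delivery and first postpartum ocrelizumab as continuous and categorical", with a last category of more than 6 months.

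**The concern.** The label and the definition disagree. A date called last contact should not fall after the woman has left the study, yet none of the three listed dates is her own last contact. A programmer who follows the definition will credit up to 182 days of risk window after the final visit, a withdrawal or a loss to follow-up.

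Two things are at stake. The exposure table would present time without routine AE collection as if it were ordinary on-treatment time. And no planned output says how many dosed women were actually followed through the SAP's own 182-day window, which is what a reader needs in order to judge a low count of late events.

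**Working it through.** **Inputs from the documents.** The 182-day window and the duration formula are in SAP 4.8.1. Infusions every 6 months and follow-up to about 13 months of infant age, with a +30-day window on the last visit, are in Protocol 3.1.4. Enrolment of about 16 months and participation of about 17 months are in Protocol 3.2.

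**The plan's own figure.** 26 weeks × 7 = 182 days, and 6 × 30.4375 = 182.6 days, so the stated equivalence of 6 months and 182 days reproduces.

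**Assumptions.** The last visit is at day 395 (13 months) or day 425 (with the 30 days added), doses are 182 days apart, no woman dies and the cut-off does not bind.

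**Formulas.**
- Credited weeks = (last dose day + 182 − first dose day + 1)/7
- Observed weeks = (earlier of that end day and the last contact day − first dose day + 1)/7
- Excess days = last dose day + 182 − last contact day, if positive

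| Dose days | Credited weeks | Observed weeks (day 395 to 425) | Excess days |
|---|---|---|---|
| 0, 182 | 365/7 = 52.1 | 52.1 | none (credit ends day 364) |
| 42 only | 183/7 = 26.1 | 26.1 | none (credit ends day 224, 171 to 201 days before AE collection ends) |
| 49, 231 | 365/7 = 52.1 | 347/7 = 49.6 to 52.1 | 18 to 0 |
| 183, 365 | 365/7 = 52.1 | 213/7 = 30.4 to 243/7 = 34.7 | 152 to 122 |
| 274 only | 183/7 = 26.1 | 122/7 = 17.4 to 152/7 = 21.7 | 61 to 31 |
| 330 only | 183/7 = 26.1 | 66/7 = 9.4 to 96/7 = 13.7 | 117 to 87 |
| 0, 182, 364 | 547/7 = 78.1 | 396/7 = 56.6 to 426/7 = 60.9 | 151 to 121 |

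**Early exit.** A woman who leaves the day after a single infusion is credited 183/7 = 26.1 weeks against 2/7 = 0.3 observed, an excess of 181 days. If she leaves four weeks after it, she is credited 26.1 weeks against 29/7 = 4.1.

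**Where the excess starts.** With two doses, it starts when the first falls after day 395 − 364 = 31, or day 425 − 364 = 61. With one dose, it starts after day 395 − 182 = 213, or day 425 − 182 = 243.

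**Does the cut-off prevent this?** The documents do not define it. If it is one study-level date at the end of the study, it falls up to about 33 − 17 = 16 months after the last visit of the earliest enrollee, and progressively less for later ones.

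**Cohort size of the effect.** This simulation assumes uniform enrolment over 16 months, a cut-off at the last infant's final visit, every woman followed to her scheduled last visit, and first doses spread uniformly over days 0 to 42, 0 to 90, 42 to 180 or 0 to 270. Total credited exposure is 1.19 to 1.30 times the total truncated at last contact if dosing continues every 182 days to the last visit. It is 1.00 to 1.25 times if there are at most two doses. The cut-off shortens the credit in about 0 to 29% of women.

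**The case against.** The best defence is that this is a treatment duration and not a follow-up time. Infusions are 6 months apart, so last dose plus 182 days covers one dosing interval, and a woman's last study visit does not end her exposure to a commercial product. That is a reasonable convention in itself. It does not fit a date named last contact that is already truncated at death and at the data cut-off, since truncation at the cut-off is a limit on what was observed.

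Other parts of the defence stand:

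- A reader might infer that every mother is credited 182 unobserved days. The documents do not support that. The rule takes the earliest of three dates, undosed women have no duration, women with only early doses have no excess, and for some the credited time ends well before AE collection does.
- A reader might also infer that the planned AE results are biased low. SAP 4.8.2 plans event totals and numbers of subjects with at least one event, with no person-time denominator. Protocol 6.5 mentions incidence rates but defines no denominator, and SAP section 4 says that its analyses supersede the protocol's.
- Late restarts and withdrawals are not concealed. The SAP tabulates time to first postpartum dose, number of doses, the interval between the first two doses, and discontinuations with reasons. What is missing is coverage of the 182 days.
- The percentages depend on the scenario. When MMR is given, the last visit is tied to the vaccine dose, with no stated upper age, so it can be earlier or later than day 395 to 425.

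**Conclusion.** The point holds for a defined subset: women dosed postpartum whose participation ends less than 182 days after their last infusion and before the cut-off. For them the reported duration includes time with no routine AE collection, although related serious events remain reportable. Under the assumptions shown, the individual excess runs from 0 to about 26 weeks, and total credited exposure is about 1.0 to 1.3 times observed. These are ranges over assumed dosing and visit dates, not estimates for this cohort.

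Bias in AE rates is conditional. It arises only if the rates in Protocol 6.5 are built on this duration. The issue concerns a descriptive maternal safety summary and does not touch the primary endpoint, infant B-cell levels at Week 6. It is still worth correcting before the exposure table is produced, because the text as written yields a figure that its own label contradicts.

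**What to change.** 1. In SAP 4.8.1, add a fourth item to the earliest-of list: date of last study contact (last visit, withdrawal or loss to follow-up). Define the Clinical Cut-off Date in the same place.
2. Add one row to the exposure table: the number and percentage of dosed women whose AE follow-up covered the full 182 days after their last infusion.
3. If any post-ocrelizumab AE incidence rate is produced, end the event-counting window and the person-time at the same date. The capped duration should not simply be reused as the denominator. The post-ocrelizumab AE window in SAP 4.8.2 has no end, so for a woman with one early dose, later events would be counted without matching time and the rate would be too high.

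The cost is one SAP line, one definition, one table row and, if rates are reported, one sentence on person-time. No new data are needed and treatment is unaffected. The downside is that the stated exposure becomes shorter.
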